**TABLE OF CONTENTS –**

Specific Aims	1
Background and Significance	2
Preliminary Studies/Experience	2
Research Design and Methods	3
Protection of Human Subjects	5
References	9

**A. SPECIFIC  
AIMS**

---

The primary aim of this pilot study will be to develop a clinically meaningful, patient-centric, and pragmatic protocol to evaluate the comparative effectiveness of different modalities for achievement of the ideal balance between analgesia and functional mobility following total knee arthroplasty (TKA).

We propose a study by which focused ***patient-centered*** inquiry will quantify the relative value of various outcome measures believed to be most meaningful to this patient population. Emphasis on patient experience and guided reflection combined with objective data will establish the optimal methodology for comparing different techniques of perioperative analgesia. We will identify those outcome measures that most accurately reflect the overall patient experience as well as the clinical result. Patient input has been conspicuously absent from previously published work on this topic, and we propose a mechanism by which the patients in cooperation with the investigators will guide the research, and ultimately clinical care.

In addition to applying a patient-centric perspective towards the identification of meaningful outcome measures, we intend to establish the ***feasibility*** and ***cost-efficiency*** of our study design and protocol. Ease of implementation, and seamless integration of clinical measures and data collection into routine workflow is necessary in order for the protocol to be attractive to other centers as part of a future multi-center trial. Previous orthopaedic surgery randomized controlled trials have set the precedence that such studies can be completed in an economical manner when such aspects of design are carefully considered(21). Through promotion of collaborative relationships between and continued engagement of the orthopaedic, anesthetic, nursing, and postoperative rehabilitative teams, the final protocol will allow all participants – care givers and patients alike - to feel invested and unburdened by the process.

Though the primary goals of the project pertain to establishment and application of proper scientific methodology to the clinical query addressing the most efficacious method

of perioperative analgesia for TKA patients, we do expect to produce clinically meaningful, if not statistically significant findings. We expect the study to be adequately powered to establish estimates of variance that will help refine subsequent power analyses for outcome measures that may not yet have precedence in the literature.

At the conclusion of this pilot study, we hope to have compiled valuable experience and knowledge, established collegial relationships across a number of disciplines, and effected a mechanism of meaningful patient engagement in design of a study that will be well-positioned to compete for the expected Patient-Centered Outcomes Research Institute (PCORI) funding via the Large Pragmatic Studies to Evaluate Patient—Centered Outcomes opportunity in the Spring of 2016

## **B. BACKGROUND AND SIGNIFICANCE**

---

According to the CDC, over 700,000 TKA's are performed in the United States annually. That number continues to rise exponentially, and is predicted to eclipse 3 million procedures by 2030(14). Though 98% of patients report pain relief following TKA, unfortunately up to one-third fail to achieve significant functional improvements (7). Nearly 20% of primary TKA patients report they are dissatisfied with their outcome, and up to 33% experience some residual symptoms (4, 17). Various associative factors have been suggested to influence outcome, ranging from socioeconomic factors, to depressed mood, age, gender, suCarolinargical technique, and comorbid conditions(3, 13).

The early postoperative period following total knee arthroplasty is widely believed to be critically important for regaining range of motion and mobility in order to optimize the ultimate clinical outcome and minimize the risk of complications including venous thromboembolic events(15). Perioperative analgesia for TKA patients has evolved considerably since the popularization of the procedure decades ago. Historically, perioperative interventions such as general anesthesia and patient-controlled analgesia pumps (PCAs) have aggressively treated postoperative pain, but have been associated with side effects including lethargy, somnolence, nausea, and mental status changes, all of which have a detrimental effect on early mobility. Furthermore, contemporary emphasis on value in healthcare has led to efforts to promote "rapid recovery" programs that facilitate early mobilization and discharge, thereby reducing total costs to the health care system. Recent trends in perioperative analgesic strategies may be related to these evolving priorities(5, 11).

Recently, with growing appreciation of the importance of early mobilization in addition to pure pain control, centers across the country have trended away from general anesthesia and PCA's in favor of regional anesthetic techniques(5). A wide range of strategies have emerged, most of which combine either spinal or epidural anesthesia with a spectrum of peripheral nerve blockade techniques and/or periarticular analgesic injection formulations(3). Unfortunately, the rate of institution of these varied modalities has outpaced the scientific evidence to support any one strategy over another. Multiple randomized trials have been published comparing one combination of interventions against another with little consistency, reproducibility, or generalizability in either methodology or results(1, 2, 8-10, 12, 16, 18-20, 22-24). The primary outcome measure

for most of these studies has been early post-operative pain levels, measured either directly via a visual analog scale (VAS), or indirectly via quantification of analgesic medication requirements(1, 2, 8-10, 12, 16, 18-20, 22-24). Most of these studies have failed to report outcomes beyond the typical 2 or 3 day hospital stay(1, 2, 8-10, 12, 16, 18-20, 22-24). Only one study that we are aware of has presented patient reported outcomes (PROs) using a validated measure, the Knee Society Score, and that was only recorded at discharge (22). Increasingly studies have reported secondary outcomes to include objective functional measures such as the Timed-up-and-go (TUG) (7, 19). Functional and patient reported outcomes beyond the immediate postoperative period are lacking in the literature. The proposed study will address these evidence gaps.

### **C. PRELIMINARY STUDIES/EXPERIENCE**

---

During residency training at the University of Massachusetts Medical School, [name] elected to pursue a "research-track", which consisted of an additional year of training exclusively dedicated to research. Specifically, during that year [name] worked extensively to help develop the infrastructure that would ultimately become the NIH-funded FORCE-TJR. Additionally, he coordinated a prospective randomized control trial using radiostereometric analysis to quantify polyethylene wear and femoral stem migration differences between conventional and highly-cross-linked polyethylene liners in total hip replacement patients. Subsequently, productive research efforts have included an award-winning project resourcing the Nationwide Inpatient Sample database to characterize national trends in total joint replacement.

[name] interest in research began during his undergraduate years when he spent two years in a Drosophila lab. His primary project during that time involved isolation of a gene important in neural development in Drosophila. He presented this research at the North Carolina Academy of Science Meeting and received an award. During medical school [name] worked on a project to culture human keratinocytes to produce skin grafts for burn patients. Currently [name] has active projects that include development of a novel regional anesthetic technique and the evaluation of regional anesthetic techniques for post-operative pain management in mastectomy patients.

[name] has previously served as a successful mentor for more junior faculty, and has demonstrated both interest and ability to secure extramural research funding. In support of this application as a mentor, [name] has recommended quarterly mentorship meetings. These meetings will address study progress via benchmarks including the pace of recruitment, enrollment, and follow-up. Preliminary analyses will be prepared in advance of and reviewed at the mentorship meetings. Barriers, challenges, and opportunities for improvement in the process will be discussed, not only for the current project, but also with an eye towards optimizing subsequent study design in advance of planned application for PCORI funding. Of particular relevance, [name] is the PI for a comparative effectiveness trial that has passed initial review for PCORI funding and is in the final stage prior to acceptance.

[name] & [name]'s strong foundational experiences combined with [name] exemplary track record of success suggests potential for a productive partnership and sound study leadership. With the proposed timetable of extramural funding during the calendar year following the pilot study, the expectation is that the mentor-mentee relationship will remain necessary for initiation of a multi-center trial, but investigator independence will gradually be achieved during the course of that trial.

## **D. RESEARCH DESIGN AND METHODS (including data analysis)**

---

All **primary** TKA patients undergoing surgery at the Medical University of South Carolina (MUSC) will be offered the opportunity to participate in the study. Those with valgus deformity greater than 10 degrees on plain radiographs will be excluded from the study. Participants will be reflective of the population of TKA candidates at MUSC, and will include adults over the age of 18 of both genders and all races. Consenting patients will all receive spinal anesthetic, and will be randomized to one of three arms: 1) Continuous femoral nerve catheter plus single injection sciatic nerve block, 2) Adductor canal catheter plus selective tibial nerve block, and 3) Adductor canal catheter alone. Patients unable to receive spinal anesthetic will be excluded. All patients will receive a standardized multimodal pain regimen and early mobilization.

**Preoperative data** will include basic demographics, visual analog pain scale (VAS) score, range of motion, body mass index (BMI), primary insurer, coronal angular deformity, and baseline opioid use. Surgical data will include tourniquet time and implant type. Time spent in pre-operative holding area, the operating room, and the post-anesthesia recovery unit will be recorded. SF-12, Patient Reported Outcomes Measurement Information System (PROMIS), and Knee Injury and Osteoarthritis Outcome Score (KOOS) will be collected as part of our participation in the Function and Outcomes Research for Comparative Effectiveness in Total Joint Replacement (FORCE-TJR).

The primary outcome measure will be postoperative visual analog pain scale (VAS) score area under the curve (AUC) for 48 hours, recorded every six hours. Pain will be measured indirectly via total in-hospital opioid consumption. Functional outcome measures will be administered by members of the physical and occupational therapy team, who typically evaluate and treat patients once on the day of surgery and twice daily each day thereafter. They will document the patient's ability to perform independent terminal knee extension and grade knee buckling with ambulation on a scale of 0-2 during each encounter. Additionally, in the morning of postoperative day #1, a Katz Index of Independence in Activities of Daily Living score will be calculated. On the morning of postoperative day #2, the therapist will document distance walked by the patient, passive range of motion (flexion and extension), a timed up-and-go test (TUG), and calculate the AM-PAC (Activity Measure for Post-Acute Care) score. Patient reported outcome measures, specifically SF-12, PROMIS, and KOOS will be collected at 6 weeks and 3 months postoperatively. These time points are not included in the FORCE-TJR registry, and therefore will be independently collected and stored. Postoperative complications will be recorded. Finally, a brief survey will be administered at 3 months, presenting inquiries regarding satisfaction with the hospital stay, pain control, mobility, and the overall TKA experience. These inquiries will pose each question with a 0-10 scale, and respondents will be asked to select the number that corresponds to their level of satisfaction with each domain of their experience.

Via partnership with the FORCE-TJR, collection of patient-reported outcomes (PRO) data for arthroplasty patients at MUSC is both well-established and sophisticated. These data will be available as baseline measures for this project. Preoperative data are collected at a mandatory appointment 2-3 weeks in advance of elective arthroplasty. At that appointment and again at follow-up, our research coordinator facilitates patient recruitment and participation with the FORCE-TJR using validated computerized survey

instruments. Additionally, for this study, she will assist with enrollment, consent, extraction of clinical data from the EPIC-EMR, and coordination of prescribed follow-up. Postoperative SF-12, PROMIS, and KOOS are collected at 6 months and 1 year via the FORCE-TJR, therefore the coordinator will additionally facilitate collection of these instruments at 6 and 12 weeks, as well as the satisfaction survey. If, in the surgeon's opinion, the patient is doing well after surgery and does not have to return to clinic at the specified time points, the surveys will be mailed to the patient with instructions on how to complete them. The study coordinator will be available to field study-related patient questions in clinic and via telephone.

At three months, a random subset of four patients from each randomization arm will be invited to participate in a focus group. The purpose of the focus group will be to facilitate patient engagement with the hope of fulfilling our primary aim of this study, which is to identify the most meaningful outcome measures for perioperative analgesia among the TKA patients themselves. Qualitative data obtained during the recorded session will prompt discussion related to the overall patient experience in addition to individual experiences related specifically to analgesia, postoperative mobility, transitioning to the out-patient setting, and involvement in a randomized trial. The focus group will be held several months after surgery, on the MUSC campus in a private room. Audiotape of the focus group will be available to relevant study personnel only, and will be kept under lock and key within an office in the Department of Orthopaedics. A preference survey will be developed and distributed for additional patient feedback.

Though the main goal of conducting this pilot study is one of establishing the appropriate data points and testing the feasibility of such a design, we will conduct some preliminary hypothesis testing. Tests on the effect of treatment upon outcomes will be performed using an intent-to-treat analysis. Preliminary estimates suggest the study will be adequately powered to detect a significant VAS difference of 2 at 25 subjects per group. However, prior research suggests that the anticipated group differences may be much subtler, requiring a very large sample size to thoroughly address the issue of which treatment is superior to the others. As a preliminary step towards a larger, more definitive comparative effectiveness trial, we plan to enroll approximately 90 patients. This will allow us to reach our randomization goal of at least 75 patients while taking into account withdrawals. The 75 patients will be randomized into the three treatment arms over a 6-month recruitment period, with a 3 month follow-up for patient reported outcome and satisfaction data. This sample will allow us to estimate means relatively precisely, with 95% confidence intervals extending just 0.4 standard deviation units in either direction. We will also be able to make preliminary estimates of each treatment's effectiveness on the various outcomes of interest. Such estimates can be made using generalized linear mixed models (GLMMs)(6). Effect sizes will then be estimated from the GLMMs in a pairwise manner, and this information will be extremely valuable for use in designing a larger, more definitive trial in the future.

The study timeline calls for initiation in April of 2015, and completion of enrollment in October, 2015. Three-month follow-up data will be collected by the end of January, 2016, which will allow for data analysis and interpretation in advance of PCORI Letter of Intent, anticipated to be due in spring of 2016.

We expect to demonstrate sound scientific methodology and a fully invested multi-disciplinary team that will define clinically meaningful though perhaps not statistically significant differences in efficacy, safety, patient-reported and objective outcomes associated with various strategies of perioperative TKA pain management. With continued

patient engagement, this pilot study will support development of a multi-center randomized comparative effectiveness trial that we expect will be strongly considered for extramural funding through the Patient Centered Outcomes Research Institute (PCORI) via the "Large Pragmatic Studies to Evaluate Patient-Centered Outcomes" Funding Announcement. As a proposed randomized trial examining a poorly defined aspect of treatment that could affect nearly one million Americans per year, such a proposal meets the stated objectives outlined in the RFA. This pilot study will allow us to present a well-formulated, novel, scientific protocol supported by experience and data. Furthermore, it will allow us to demonstrate commitment and capacity for patient engagement in the study design process. The ultimate goal after procurement of extramural funding is to expand and establish this methodology as the generalizable gold standard for comparative effectiveness studies assessing perioperative TKA analgesia, and foster the development of a healthcare learning environment capable of identifying the most optimal strategy for perioperative TKA analgesia.

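### The day-2 mobility tests have no fallback for a patient discharged earlier, and discharge time is not collected: a cheap safeguard, not a demonstrated bias

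*Protocol*

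**What the plan says.** Protocol Section D gives four functional measures a single time point. It begins "On the morning of postoperative day #2, the therapist will document distance walked by the patient", adds passive range of motion, and ends with "a timed up-and-go test (TUG), and calculate the AM-PAC (Activity Measure for Post-Acute Care) score". Section E.1.b (Sources of Materials) repeats the schedule. The assessors are the physical and occupational therapists, "who typically evaluate and treat patients once on the day of surgery and twice daily each day thereafter". Neither section says what happens if the patient has left before that session.

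Some function is captured earlier. Therapists record terminal knee extension and "grade knee buckling with ambulation on a scale of 0-2 during each encounter", and a Katz score is taken on the morning of day 1.

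On durations, Section D says "Time spent in pre-operative holding area, the operating room, and the post-anesthesia recovery unit will be recorded". Discharge time, length of stay and discharge destination appear in no data list. The only item that mentions the stay is a satisfaction rating at 3 months. Opioid use is a total over the time in hospital.

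Section B describes rapid-recovery "programs that facilitate early mobilization and discharge, thereby reducing total costs to the health care system", and refers to the "typical 2 or 3 day hospital stay" when discussing published studies.

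**The concern.** A patient who goes home before the day-2 session has no walking distance, range of motion, TUG or AM-PAC value. Fitness for discharge probably depends on the mobility these tests measure, so the missing patients would tend to be the best performers. If one arm speeds recovery, it would lose more of its best values than the others and its advantage would look smaller. No recorded length of stay would show the benefit in another way.

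The analysis could do little to repair this. Walking distance, TUG and AM-PAC have one postoperative reading, and Section D lists no preoperative value for them, so a mixed model has no other reading on the same instrument to borrow from. Assessment times and collected fields are set in the protocol, so this is not a detail to leave to an analysis plan.

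A second point does not depend on anyone leaving before day 2. An in-hospital opioid total grows with the length of the stay. Without a discharge time, a lower total from better analgesia cannot be told apart from a lower total due to going home sooner.

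Section D says that pairwise effect sizes from this pilot will be used to design the larger trial, so both points would carry forward.

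**Working it through.** **1. Are patients likely to be present?** A 2-day stay ends on day 2. If the 48-hour pain window starts at the end of surgery, it closes on day 2 at the clock time surgery ended. Both suggest that the plan expects patients in hospital that morning. Section E.2.b leaves routine postoperative care unchanged apart from extra data collection, so nothing guarantees it. The documents give no discharge distribution.

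**2. The plan's own precision figure.** Section D states 95% intervals of 0.4 SD either way. With 25 per arm: 1.96/√25 = 0.392 SD (normal) or 2.064/√25 = 0.413 SD (t, 24 df). Both round to 0.4, so the figure is reproduced. If 20% of an arm had no day-2 value: 1.96/√20 = 0.438 SD. The loss of precision is modest.

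**3. Size of a possible bias (all inputs assumed).** Take TUG in SD units, lower being better: N(0, 1) in the slower arm and N(−0.5, 1) in the faster. A readiness index has correlation ρ with TUG, and a patient leaves early if the index is below c = Φ⁻¹(p), where p is the share leaving early in the slower arm. Among those still present:

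- slower-arm mean = ρφ(c)/(1 − p)
- faster arm: c′ = c + 0.5ρ, share leaving q = Φ(c′), mean = −0.5 + ρφ(c′)/(1 − q)

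For ρ = 0.5 and p = 5%: c = −1.645 and the slower mean is 0.054; c′ = −1.395, q = 8.2% and the faster mean is −0.418. The observed difference is 0.054 + 0.418 = 0.472.

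The standard error of a two-arm difference at 25 per arm is √(2/25) = 0.283 SD, a 95% half-width of 1.96 × 0.283 = 0.55 SD.

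| ρ | p | q | Observed difference (true 0.5) | Shortfall | Shortfall / 0.283 |
|---|---|---|---|---|---|
| 0.5 | 5% | 8% | 0.47 | 0.03 | 0.10 |
| 0.5 | 10% | 15% | 0.46 | 0.04 | 0.14 |
| 0.5 | 20% | 28% | 0.44 | 0.06 | 0.20 |
| 0.7 | 5% | 10% | 0.44 | 0.06 | 0.20 |
| 0.7 | 10% | 18% | 0.42 | 0.08 | 0.29 |
| 0.7 | 20% | 31% | 0.39 | 0.11 | 0.40 |

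The faster arm would lose about 2 (8%) to 8 (31%) of its 25 values. At p = 0 the shortfall is zero.

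**4. Sensitivity to the model.** If the readiness index itself shifts by the full 0.5 SD between arms, with correlation 0.6, then p = 5%, 10% and 20% give q = 13%, 22% and 37%, and observed differences of about 0.42, 0.39 and 0.35 SD. The last shortfall, 0.15 SD, is about 0.5 of a standard error. The direction is the same in both models; the size is not fixed by anything in the documents.

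**5. Opioid total.** At a constant daily rate, a 3-day stay gives 3/2 = 1.5 times the total of a 2-day stay, with no difference in analgesia. The ratio is smaller if use falls during the stay.

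**The case against.** The strongest reply is that the bias may be empty. The stay described as typical and the 48-hour pain window both reach the morning of day 2, every arm has a catheter, and therapists plan to see patients twice daily. That the tests exist only for inpatients is itself inferred from the therapists' role. All of this stands, and it rules out calling the mobility comparison biased.

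Even on the assumed figures, the shortfall in the table is 0.10 to 0.40 of a standard error, on non-primary outcomes in a pilot that calls its testing preliminary. This also stands, although the alternative model gives somewhat more.

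A reader might infer that omitting length of stay contradicts the protocol's aims. The documents do not support that. Section B mentions discharge when describing rapid-recovery programs generally. Section A aims at the balance of analgesia and mobility, and its cost-efficiency is that of the study design.

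Early function is partly covered by the knee extension and buckling records and the day-1 Katz score. Length of stay could probably be recovered from the electronic record, but it is not named among the data to extract.

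Finally, testing the fastest patients sooner has its own bias: they are measured at an earlier stage of recovery. This is correct, and the fix has to allow for it.

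**Conclusion.** Two facts are established. The four day-2 measures have no fallback for an earlier discharge, and no discharge time or length of stay is collected. The consequence is conditional: any patient who leaves before the session is missing for a reason probably related to recovery, which would understate a faster-recovering arm.

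A reader might go further and conclude that early discharge will distort the mobility results. That needs an appreciable share leaving before day 2. The documents do not give the share, and their timing suggests it is small. The range of 0.47 to 0.39 SD against a true 0.5 SD rests wholly on the assumed early-discharge share, effect and correlation.

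The dependence of the opioid total on length of stay needs no early leavers, only stays that differ between patients. This is a low-priority improvement, worth making because it is cheap and because the pilot's stated main goal includes settling which data to collect.

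**What to change.** - **Assessment time.** In Sections D and E.1.b, schedule the four tests for the day-2 morning, or for the last therapy session before discharge if that comes first. Record the time since surgery and the reason for any missing test.
- **Reporting.** State how many tests were taken early in each arm, and show results with and without them. Adjusting for recorded time is not a full correction, because that time is itself a consequence of recovery after randomization.
- **Length of stay.** Add discharge date and time to the data the coordinator extracts from the electronic record, and report length of stay by arm as a secondary outcome.
- **Opioid use.** Present it over a common fixed window, for example the 48 hours already used for pain, or alongside length of stay. Identify patients who left before the window closed.

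The cost is one clause in the schedule, a few data fields, and notice to the therapist when a discharge is planned before day 2. A few tests will come from an earlier stage of recovery. Nothing here alters when a patient is discharged.
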